The long-term goal of our transdisciplinary team is to develop, evaluate, and disseminate new diabetes prevention strategies targeting novel psychosocial risk factors. This project's objective is to perform a preliminary evaluation of the efficacy of our existing primary care-based intervention for depression (eIMPACT-DM) in improving diabetes risk markers. eIMPACT-DM is a modernized collaborative stepped care intervention consisting of (1) computerized and telephonic cognitive-behavioral therapy (CBT) for depression and (2) select antidepressant medications included in an algorithm optimized for diabetes risk reduction. Our preliminary data (see C2) establish the feasibility and antidepressive efficacy of eIMPACT-DM. We propose a pilot RCT of 64 primary care patients with a depressive disorder and prediabetes. Patients will be randomized to 6 months of eIMPACT-DM or the active control (depression education, symptom monitoring, and primary care for depression). The primary outcome is hemoglobin A1c – the gold standard glycemic outcome,⁶⁸ a strong predictor of diabetes development,^{69,70} and a potent indicator of improvement in diabetes endpoints.^{5,69,71,72}

Primary Aim: Determine the preliminary efficacy of eIMPACT-DM in improving diabetes risk markers among depressed primary care patients with prediabetes. Depressed patients randomized to eIMPACT-DM, versus the active control, will exhibit greater improvement in A1c (primary outcome; H1) and insulin resistance (HOMA score; secondary outcome; H2) from pre-treatment to post-treatment 6 months later.

Exploratory Aim: Explore whether the effect of eIMPACT-DM on diabetes risk markers is greater among patients with a somatic presentation of depression at pre-treatment (baseline) than among patients without such a presentation. A somatic presentation of depression at baseline is defined as having hyperphagia (increased appetite/weight) and/or hypersomnia (increased sleep) at pre-treatment. Our preliminary data (see C3) suggest that, in people with depression, those with hyperphagia (increased appetite/weight) and/or hypersomnia (increased sleep) are a subgroup at particularly elevated diabetes risk. Because our findings raise the intriguing possibility that this subgroup may show greater improvement in diabetes risk markers after depression treatment, we will explore if effect sizes for eIMPACT-DM on A1c and insulin resistance are larger for patients with versus without hyperphagia and/or hypersomnia.

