3.0 Outcome Measures/Endpoints

Primary Outcome (A1c)

The primary outcome is 6-month change in hemoglobin A1c. A1c will be measured at pre- and post-treatment by an immunoturbidimetric method on a Randox Daytona Clinical Analyzer in the Translation Core Analyte Lab of the Indiana CTSI. A1c is the best choice for our primary outcome for many reasons. First, A1c is considered the gold standard assessment of glycemic control and is a common surrogate endpoint in diabetes trials.¹⁶ Also, A1c $\geq 6.5\%$ is diagnostic of diabetes.⁸⁶ Second, A1c strongly predicts future diabetes.¹⁷ A systematic review¹⁸ found that the 5-year incidence of diabetes increased sharply with A1c, from <9% incidence for A1c 5.0-5.5% to 9-25% incidence for A1c 5.5-6.0% and 25-50% incidence for A1c 6.0-6.5%. The diabetes incidence rate for A1c 5.0-5.5%, 5.5-6.0%, and 6.0-6.5% was approximately 2 times, 5 times, and 20 times greater than for A1c <5.0%, respectively.¹⁸ Third, interventions producing A1c improvements have been shown to also improve clinical diabetes endpoints,^{19,20} and diabetes prevention interventions targeting glycemic control result in reduced rates of progression from prediabetes to T2D.^{8,17} Thus, A1c is associated with clinical benefit. Fourth, A1c has statistical advantages. As a continuous measure, it provides greater statistical power than clinical events and thus requires smaller samples and shorter follow-ups. Also, because A1c reflects average glucose over the preceding 90-120 days,¹³⁹ it is more stable than alternative measures, such as fasting glucose and oral glucose tolerance tests.⁸⁶ For all of these reasons, A1c is well suited to evaluate if a new intervention approach holds promise, and it is appropriate and feasible for pilot trials.

Secondary Outcome (HOMA Score)

The secondary outcome is 6-month change in insulin resistance, as indicated by HOMA score. HOMA scores⁸⁰ will be derived from fasting glucose (glucose oxidase method on a Randox Daytona Clinical Analyzer) and insulin (two antibody immunoassay on a Roche cobas e411 Analyzer). Fasting glucose and insulin assays will be performed in Translation Core Analyte Lab of the Indiana CTSI. HOMA score is an established index of insulin resistance that correlates highly with the more invasive euglycemic clamp ($r=0.85-0.88$) and is appropriate for assessing change.¹¹¹⁻¹¹⁴

Exploratory Outcome (Incident Diabetes)

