11.0 Statistical Considerations

Sample Size Justification and Power Analysis

This pilot RCT is not designed to detect statistically significant differences. We chose N=64, as it is sufficient to yield the expected outcomes and is feasible within the R21 constraints. Assuming an attrition rate of $\leq 20\%$,¹¹⁷ we will have ≥ 50 completers (25/arm). With 50 completers and type I error rate=5%, we will have 55%, 68%, 79%, and 88% power to detect a $d=0.60, 0.70, 0.80$, and 0.90, respectively. We observed a $d=0.90$ for CBT for depression on fasting glucose in depressed primary care patients (see C2).

Primary Aim Analytic Plan

Analyses will use the intent-to-treat approach.¹¹⁸ Tests will be two-tailed with $p<.05$ considered statistically significant. Supplemental analyses of completers and analyses employing multiple imputation (SAS mi and mianalyze) will be performed. We will assess for group differences in baseline factors. Due to randomization, we do not expect differences. Even so, baseline differences will be taken into account when interpreting results, and baseline factors that differ between groups will be added as covariates in sensitivity analyses. We will also add expectancy and attention as covariates in sensitivity analyses.

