We will evaluate H1 and H2 (eIMPACT-DM patients will exhibit greater improvement in A1c and HOMA score) using linear mixed modeling (SAS proc mixed) with an unstructured covariance matrix. Subject will be a random effect, and treatment group, time, and their interaction will be fixed effects. Separate models will be run for the primary (A1c) and secondary (HOMA score) outcomes. Treatment group x time interactions would indicate statistically significant treatment effects. For both A1c and HOMA score, we will report the group means and standard errors; regression coefficients, 95% CIs, and p-values; and effect sizes (d 's). We will consider an absolute group difference in post-treatment A1c of $\geq 0.3\%$ ($d=0.50$) to be clinically important (e.g., 5.9% for eIMPACT-DM group versus 6.2% for AC group; $d=0.50$). This A1c difference corresponds to annualized diabetes incidence rate of 4.0% for the eIMPACT-DM group versus 7.0% for the AC group.⁷⁰ Because there is no absolute cut point distinguishing between normal and abnormal HOMA scores,¹¹⁹ we will consider a $d\geq 0.50$ (moderate effect size⁶⁵) as clinically important. If we find that the eIMPACT-DM produces clinically important improvements in A1c and HOMA score (d 's ≥ 0.50), it would pave the way to an R01-level RCT by (1) generating critical proof-of-concept data to support the premise and (2) providing preliminary effect sizes for eIMPACT-DM on A1c and HOMA score. Of note, the effect size estimate used in the primary power analysis for the future RCT will be based on the minimal clinically important difference in A1c instead of solely on this RCT's results, as pilot studies tend to overestimate or underestimate true effect sizes.¹²⁰ We will use this RCT's results, along with other relevant data, to make a strong case that the selected effect size estimate is plausible and achievable.

A set of planned subgroup analyses will be performed including only participants with pre-treatment A1c values between 5.70%-6.49%. Another set of planned subgroup analyses will explore whether history of COVID-19 infection (defined as history of a positive COVID-19 test at trial entry) moderates the effect of eIMPACT-DM on A1c and HOMA score.

Exploratory Aim Analytic Plan

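### H1 is tested on the between-arm difference in A1c change, but the 0.3-point importance threshold is set on the post-treatment difference, so a chance baseline gap can make the label and the test disagree

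*Combined protocol and SAP*

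**What the plan says.** Section 3.0 defines the endpoint as a change: "The primary outcome is 6-month change in hemoglobin A1c". Section 2.0 frames H1 in the same way, as greater improvement from pre- to post-treatment in the eIMPACT-DM arm.

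Section 11.0 (Primary Aim Analytic Plan) specifies the model: "Subject will be a random effect, and treatment group, time, and their interaction will be fixed effects". It then names the test: "Treatment group x time interactions would indicate statistically significant treatment effects". Baseline A1c is not a covariate, and the arms are not constrained to a common baseline mean.

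The same paragraph sets the importance rule on a level: "We will consider an absolute group difference in post-treatment A1c of" at least 0.3 points, labelled d=0.50 and illustrated by post-treatment values ("5.9% for eIMPACT-DM group versus 6.2% for AC group"). It ties those two levels to annual diabetes incidence of 4.0% and 7.0%. It then returns to the wording of change: "If we find that the eIMPACT-DM produces clinically important improvements in A1c and HOMA score", with d of at least 0.50 on both outcomes, the result would support the larger trial.

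Two other provisions bear on baseline balance. Sections 5.0 and 7.0 stratify randomization by A1c in two bands (up to 6.09%, and 6.10-6.49%). Section 11.0 says that baseline differences will inform interpretation and that differing factors will enter sensitivity analyses as covariates.

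**The concern.** The quantity that is tested and the quantity that is labelled are not the same. In this model they differ by exactly the between-arm gap at baseline. A result can therefore be called clinically important when the tested effect is well below 0.3, or unimportant when the tested effect reaches 0.3, for a reason unrelated to treatment.

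This matters because Section 11.0 says that the pilot is not designed to detect statistically significant differences. The importance label therefore carries much of the proof-of-concept argument for the larger trial, and it should describe the effect that the trial estimates.

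**Working it through.** **Inputs from the plan.** 25 completers per arm; two-sided 5%; threshold 0.3 points, called d=0.50; the model above. The implied SD is 0.3/0.50 = 0.6. The plan gives no other A1c SD and no pre-post correlation.

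**The plan's own figures.** A two-sample t-test with 25 per arm (48 df) has power of 54.7%, 67.9%, 79.2% and 87.7% at d=0.60, 0.70, 0.80 and 0.90. The plan states 55%, 68%, 79% and 88%, so its figures reproduce and 25 per arm is the right basis.

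**Identity.** Write every difference as control minus eIMPACT-DM, so that positive favours eIMPACT-DM. Let G be the baseline difference, P the post-treatment difference and C the difference in improvement (group x time). Then P = C + G.

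| | Baseline (eIMPACT-DM, control) | Post (eIMPACT-DM, control) | G | P | C |
|---|---|---|---|---|---|
| Case 1 | 5.95, 6.10 | 5.90, 6.20 | 0.15 | 0.30 (important) | 0.15 |
| Case 2 | 6.05, 5.95 | 5.85, 6.05 | -0.10 | 0.20 (not important) | 0.30 |

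**Size of a chance gap.** Without balancing, SD(G) = baseline SD x sqrt(2/25):
- SD 0.23: 0.065
- SD 0.30: 0.085
- SD 0.40: 0.113
- SD 0.60: 0.170

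With allocation balanced within two A1c strata, simulation lowers this to about 0.04 (SD 0.23) to 0.11 (SD 0.60). Against a threshold of 0.3, gaps of 0.05-0.15 are ordinary in most of these settings.

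**How often the rules disagree at a true effect of 0.3.** Both quantities are then centred on the threshold. Without balancing, the probability that they fall on opposite sides is arccos(r)/pi, where r is the correlation of P and C. For equal SDs and pre-post correlation rho, r = sqrt((1 - rho)/2).
- rho 0.5: r = 0.500, disagreement 33%
- rho 0.7: r = 0.387, disagreement 37%
- rho 0.8: r = 0.316, disagreement 40%
- Baseline SD 0.23, post SD 0.60, rho 0.8: r = (0.36 - 0.1104)/(0.60 x 0.438) = 0.949, disagreement 10%

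Simulation with SDs of 0.23-0.60, post-treatment SD no smaller than baseline SD, and rho of 0.5-0.8 gives about 10-41% unbalanced, in line with the formula. With balancing within A1c strata it gives about 8-30%.

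**With no true effect.** Disagreement is at most about 4% balanced and 6% unbalanced. The largest values occur at SD 0.6 and rho 0.5 (3.3% and 5.9% in one run). They are near zero when both SDs are 0.3.

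**Which estimate handles the gap best.** With equal SDs, a gap G shifts P by +rho x G and C by -(1 - rho) x G. At rho 0.6 these are +0.6G and -0.4G, so the change estimate also carries the gap, with opposite sign. Baseline adjustment removes it. Standard errors at SD 0.6, rho 0.6, 25 per arm, unbalanced:
- Post-treatment difference: 0.6 x sqrt(2/25) = 0.170
- Difference in change: 0.6 x sqrt(2 x 0.4) x sqrt(2/25) = 0.152
- Baseline-adjusted: 0.6 x sqrt(1 - 0.36) x sqrt(2/25) = 0.136 (0.137 in simulation)

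**The case against.** Several points on the other side stand.

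- **No bias.** Under randomization both quantities have the same expected value. The high disagreement rates are taken with the true effect exactly on the threshold, where each rule passes about half the time and any two noisy estimates would often split.
- **Existing safeguards.** A1c stratification cuts the SD of the gap by roughly 35-40% in simulation, and baseline differences are to be considered in interpretation. Both help. Neither changes the threshold, and the covariates are confined to sensitivity analyses. Balance may also be weaker than simulated: randomization takes place at the pre-treatment visit, where a finger-stick value is available, while the outcome A1c comes from blood stored until assay.
- **Limited reach.** The go-forward sentence requires d of at least 0.50 on HOMA score as well, and Section 11.0 says that the future power analysis will rest on the minimal clinically important difference rather than solely on this result.
- **Purpose of a level-based rule.** The two post-treatment levels are linked to diabetes incidence, which explains the choice. It does not make the label match the test.
- **Possible unstated adjustment.** The preliminary effect sizes in Section 1.0 (C1 and C2) are adjusted for pre-treatment level, so the team may intend the same here. Section 11.0 does not say so.

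A reader might infer two stronger conclusions. The first is that arms starting at 5.9% and 6.2% and not changing at all would be called important. That follows from the wording, but a baseline gap of 0.3 in that direction is very unlikely in this design: about 0.3% of balanced trials at SD 0.6, and about 0.01% or less at SD 0.4 or below. The second is that the rule lets small true effects through more often than the tested quantity would. With equal SDs this holds only for correlations above about 0.5. At SD 0.6, correlation 0.5 and a true effect of 0.2, balanced pass rates are 25.3% (post-treatment) and 25.9% (change). The documents give no correlation, so neither inference is supported.

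**Conclusion.** The mismatch is explicit in Section 11.0 and should be corrected. The importance label rests on the tested estimate plus the chance baseline gap, so the two can disagree on the same data. For true effects near 0.3 this happens in roughly 8-30% of trials with A1c balance and 10-41% without. With no effect it happens in at most about 4% and 6%.

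These ranges assume 25 completers per arm, normally distributed A1c, SDs of 0.23-0.60 and correlations of 0.5-0.8. Only the SD of 0.6 can be traced to the plan, and only by implication. The consequence is mainly extra noise in a go-forward label. The significance test is unaffected, and nothing in the documents shows a systematic lean towards a favourable label.

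**What to change.** In the Primary Aim Analytic Plan of Section 11.0:

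- Apply the 0.3-point threshold to the baseline-adjusted between-arm difference in post-treatment A1c. This can come from a model with baseline A1c as covariate, or from the mixed model with a common baseline mean. Use that same estimate to test H1 and report it with its 95% CI.
- If the current model is kept, apply 0.3 to the group x time estimate so that test and label match, and note that this estimate still carries the baseline gap with opposite sign.
- State which SD defines d. With SD 0.6 at both visits, the SD of change is 0.6 x sqrt(2(1 - rho)): 0.60 at correlation 0.5, where 0.3 is d=0.50, but 0.46 at correlation 0.7, where 0.3 is d=0.65.
- Show unadjusted post-treatment means descriptively only.

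The cost is a sentence or two in the analysis plan and no new data. The drawback is that the label can no longer be read directly from two post-treatment means, and the 4.0% versus 7.0% incidence comparison becomes illustrative.

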B. Innovation

B1. Our trial would be the first to evaluate depression treatment as a diabetes prevention strategy.

This RCT would be the first to test the effect of a depression intervention on A1c in depressed people with prediabetes. Our focus on a psychological factor is a major departure from current prevention efforts.⁵

B2. eIMPACT-DM has innovative aspects that support broader dissemination and implementation.

Although collaborative care for depression in primary care is an established approach,⁵⁷ only one trial⁵⁸ besides our eIMPACT Trial (see C2) has incorporated computerized CBT. Moreover, no trials have used an antidepressant algorithm optimized for diabetes risk reduction. To achieve our long-term goal, large-scale dissemination and implementation must be possible. eIMPACT-DM fits very well in primary care, where behavioral health staff and space are limited, as it harnesses technology to minimize personnel and space requirements. In addition, because eIMPACT-DM uses computerized CBT, it is more scalable, easier to deliver with high fidelity, and likely more cost effective⁵⁹ than current collaborative care models. Finally, eIMPACT-DM can reach patients with logistical barriers, as many components are internet or phone delivered. Pew data show that 89% of adults (87% for non-Hispanic Blacks; 81% for lower income households) use the internet.

B3. Using a statewide information exchange to identify incident T2D is unique and has advantages.

The Indiana Network for Patient Care (INPC),^{60,61} the nation's largest clinical data repository, is a secure statewide health information exchange operated by Regenstrief Institute. In addition to extensive data provided by healthcare systems, INPC gathers data from Indiana Medicaid and commercial payers and death data from the Indiana State Department of Health. Advantages of using INPC seen in our past studies⁶²⁻⁶⁴ are an easily extended follow-up and minimal attrition (no patient participation required).

C. Preliminary Studies

C1. The Beating the Blues for Your Heart Trial (PI: [name]; ClinicalTrials.gov Identifier: NCT01605552)

This small pilot RCT provides initial proof-of-concept data. Although its primary outcome was a CVD risk marker, it allowed for a diabetes-related post hoc analysis. 29 Eskenazi Health

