The exploratory outcome is time to T2D onset, defined as the first occurrence of the following between the participant's enrollment date and five years after their post-treatment visit date: T2D diagnosis (ICD-10 E11), fasting glucose ≥ 126 mg/dL, A1c $\geq 6.5\%$, or death due to T2D. The Regenstrief programmer will identify incident T2D cases by searching INPC – the statewide health information exchange (see B3) – blinded to group assignment. Our endocrinologist ([name]), also blinded, will use standardized criteria to adjudicate all incident T2D cases. As we are doing in the eIMPACT Trial, we will obtain authorization from participants to conduct INPC searches to identify incident diabetes until five years after their post-treatment visit date. We will assess this outcome annually, with the first assessment at post-treatment. Because only a large Phase III trial would be powered for clinical events, incident T2D is an exploratory outcome. Based on our prediabetes inclusion criterion and the review described above,⁷⁰ we expect a diabetes incidence rate of $\geq 25\%$ over 5 years. [name] will use his faculty development funds (\$4K/year) and/or his research account (\$50K) to cover INPC searches after the project period.

Somatic Depressive Symptoms

Total depressive symptoms will be assessed by the 20 depression items (response options: 0-4) of the Symptom Checklist-90 (SCL-20), a reliable and valid scale,¹¹⁵⁻¹¹⁸ at the pre-

and post-treatment visit. Patients with a score ≥ 2 to the hyperphagia item and/or hypersomnia item at pre-treatment will be coded as "yes" for the presence of somatic depressive symptoms. All others will be coded as "no."

Other Factors

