To explore whether somatic depressive symptoms moderate the effect of eIMPACT-DM on A1c and HOMA score, we will rerun the Primary Aim models stratified by somatic symptoms group. We expect ~60% of patients to have hyperphagia and/or hypersomnia and thus be coded as "yes" on the somatic symptoms group variable (see C3). The remaining patients will be coded as "no." We anticipate larger effect sizes for the somatic symptoms group. We will consider an effect size difference between groups of $d\geq 0.50$ to be clinically meaningful (e.g.,

$d=0.75$ vs. 0.25). We will compute effect sizes of treatment group x somatic symptoms group x time interactions for A1c and HOMA score; however, we expect these to be nonsignificant due to lower power. If we find clinically important effect size differences between those with vs. without somatic depressive symptoms, we will modify the design of the R01-level RCT as follows – recruitment: enroll 50% with and 50% without these symptoms; randomization: stratify on presence of these symptoms; and sample size: ensure sufficient power to detect 3-way interactions.

A set of planned subgroup analyses will be performed including only participants with pre-treatment A1c values between 5.70%-6.49%. Another set of planned subgroup analyses will explore whether history of COVID-19 infection (defined as history of a positive COVID-19 test at trial entry) moderates the effect of eIMPACT-DM on A1c and HOMA score.

Incident Diabetes

We will also explore whether eIMPACT-DM patients show a clinically relevant reduction ($\geq 25\%$ lower relative risk) in incident diabetes by performing a Cox model with treatment group predicting time to diabetes onset.

Sex as a Relevant Biological Variable

In exploratory analyses, we will examine sex as a moderator of treatment effects on all outcomes by testing treatment group x sex x time interactions in the Primary Aim models. In addition, we will examine whether there is sex difference in the likelihood of being classified as having a somatic presentation of depression (i.e., those with hyperphagia and/or hypersomnia) at baseline. If a sex difference is found, it would influence the design of the future definitive RCT – e.g., we would likely additionally stratify randomization by sex.

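### Does the 25% relative-risk benchmark for exploratory incident diabetes need a stated confidence interval or a changed rule?

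*Combined protocol and SAP*

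**What the plan says.** Section 11.0 (Incident Diabetes) gives this outcome one sentence: the team will explore whether the intervention group will "show a clinically relevant reduction ($\geq 25\%$ lower relative risk) in incident diabetes by performing a Cox model", with treatment group as the predictor. It names no interval, p-value or other measure of precision. The explicit reporting commitment appears under the Primary Aim and is confined to two outcomes: "For both A1c and HOMA score, we will report the group means and standard errors; regression coefficients, 95% CIs, and p-values".

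Section 3.0 defines an event as the "first occurrence of the following between the participant's enrollment date and five years after their post-treatment visit date", the qualifying items being a T2D diagnosis, a fasting glucose of at least 126 mg/dL, an A1c of at least 6.5%, or death due to T2D. Cases are found by searching the statewide health information exchange (INPC), blind to arm, and a blinded endocrinologist "will use standardized criteria to adjudicate all incident T2D cases". On frequency, "we expect a diabetes incidence rate of $\geq 25\%$ over 5 years". On status, the section states that "only a large Phase III trial would be powered for clinical events, incident T2D is an exploratory outcome".

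**The concern.** A numerical threshold attached to the phrase clinically relevant, with no stated measure of precision, reads like a rule to be applied to the point estimate. In a trial of 64 patients that rule would be weak. Few events are expected, the hazard ratio will be imprecise, and chance alone will often carry it past 0.75. The explicit CI commitment for A1c and HOMA score makes its absence here look deliberate. At stake is a report that describes a chance difference as a meaningful reduction in diabetes, the most clinically striking outcome in the trial.

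There is also a question about what counts as incident. The event window opens at enrollment, which Section 10.0 places at the start of the pre-treatment visit. Entry is gated by a finger-stick A1c, but venous blood is stored until assay while randomization happens at the same visit. A patient could therefore be randomized with a stored A1c or fasting glucose that already meets the event definition, and no rule says how the Cox model treats that patient.

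**Working it through.** **The plan's own figures.** The protocol gives no power or precision figure for incident diabetes. Its only power statement (Section 11.0: 55%, 68%, 79% and 88% for d = 0.60 to 0.90 with 25 per arm) reproduces with a two-sided two-sample t-test: 54.7%, 67.9%, 79.2% and 87.7%.

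**Inputs.** N = 64, allocated 1:1 (Sections 5.0 and 11.0). Incidence is 25% over five years, the floor of the protocol's expectation. For an upper end, 50% is the top of the range cited in Section 3.0, "25-50% incidence for A1c 6.0-6.5" (percent). All 64 are taken as followed, because Section 1.0 (B3) credits the exchange with "an easily extended follow-up and minimal attrition (no patient participation required"). Relative risk is read as the Cox hazard ratio, which is an assumption.

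**Chance of meeting the benchmark with no effect.** With 1:1 allocation, SE(log HR) = 2/√events, and P(HR ≤ 0.75) = Φ(ln 0.75 / SE), where ln 0.75 = −0.288. The simulation column is from Cox fits (20,000 trials per setting, 32 per arm, exponential times, five years).

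| Incidence | Events (64 × incidence) | SE | P(HR ≤ 0.75), no effect | Simulated |
|---|---|---|---|---|
| 25% | 16 | 0.500 | 28.3% | 28.7% |
| 30% | 19.2 | 0.456 | 26.4% | 27.3% |
| 40% | 25.6 | 0.395 | 23.3% | 23.6% |
| 50% | 32 | 0.354 | 20.8% | 21.1% |

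**Sensitivity.**
- Window of about 5.5 years: 1 − 0.75^(5.5/5) = 27.1%, or 17.4 events, SE 0.480, chance 27.4%.
- Incidence of 15% (Section 3.0 cites 9-25% for A1c 5.5-6.0%, and such patients can enter): 9.6 events, chance 32.8%.
- Only 50 patients followed: 30.6% at 25% incidence and 23.6% at 50%.
- Relative risk read as a ratio of cumulative risks (exact binomial, 32 per arm): 27% at 25% incidence and 14% at 50%.

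**What the interval would show.** Around an observed 0.75, the 95% CI is 0.75 × exp(±1.96 × SE): 0.28 to 2.00 with 16 events and 0.38 to 1.50 with 32. For the upper limit to fall below 1, the observed hazard ratio would have to be below exp(−1.96 × 0.500) = 0.38 or exp(−1.96 × 0.354) = 0.50 respectively. Power for a true hazard ratio of 0.75 is about 8% with 16 events and 13% with 32; 80% power needs about 380 events. This agrees with the protocol's own remark that only a large trial could address clinical events.

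**Does anything depend on the label?** Section 11.0 ties the case for the larger trial to effect sizes on A1c and HOMA score, and its design to the somatic-symptom and sex findings. Section 8.0 schedules the application for that trial in the last two quarters of Year 2. Diabetes follow-up runs to five years after each post-treatment visit, so the completed result arrives after the application has been written.

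**Pre-treatment laboratory values.** Set side by side, Section 3.0 finds events through INPC and has them adjudicated. Section 12.0 sends research assay results from the core laboratory to the study team as a spreadsheet, and no route into INPC is described. Section 4.0 excludes prior EMR evidence of diabetes and codes a pre-treatment A1c of 6.5% or more as a history of diabetes. What remains unwritten is the handling of a randomized patient whose stored sample proves diabetic. The documents do not allow that number to be estimated. Because these samples are drawn before randomization, any such patients would be divided between the arms by chance.

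**The case for a change.** The strongest case for a change is that lack of power is the very reason to commit to showing precision. The protocol wrote that commitment down for A1c and HOMA score, the threshold is the only interpretive criterion offered for diabetes, and adding an interval costs a few words. The figures support this: between a fifth and just over a quarter of null trials would pass the benchmark on the estimate alone, and more if incidence falls below 25%. That arithmetic stands, as does the observation that the text is silent on an interval.

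What does not stand is the step from silence to a point-estimate rule. The sentence says the team will explore, and it names the model and a size of effect worth noticing. It does not say that crossing 0.75 settles the matter. Stating in advance what would be clinically relevant is legitimate and can be read beside an interval; removing the benchmark would be a preference on which statisticians differ. A sensitivity analysis that drops randomized patients on pre-treatment values would rest partly on a single fasting glucose, which Section 1.0 (C1) itself describes as easily disturbed by short-term influences, and no gain from it can be shown. A rule for a diabetic stored sample would be tidy, but blinded adjudication with standardized criteria is the natural place to deal with it.

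**Conclusion.** No change follows. This is missing reporting detail that analysts will fill sensibly: a Cox fit gives the log hazard ratio and its standard error, and the hazard ratio would ordinarily be reported with its 95% CI and the events in each arm. The 25% benchmark can be read against that interval.

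The 28% to 21% chance rate (27% to 14% if relative risk means a ratio of cumulative risks) applies only if the label is given on the estimate alone, which the plan does not say. It also assumes constant hazard, 25% to 50% incidence and all 64 patients followed; lower incidence or loss to follow-up would raise it. Even then the harm would be one poorly worded sentence about an outcome that the protocol already calls exploratory and unpowered, in a trial that Section 11.0 says was not sized to find significant differences and whose discussion of the primary outcomes warns that pilot effect sizes are unreliable. The question about pre-treatment laboratory values is speculative on the documents as written and has no derivable size.
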